### key words:

Estradiol, Pregnolone, Progesterone, Testosterone, Androstenodione, ovarian stimulation

## Protocol Synopsis

---

Protocol Title: Follicular Esteroidogenesis in Controlled Ovarian Stimulation

---

EudraCT Code: 2015-005762-28

---

Sponsor's protocol version and date: 1.0 of 12/1/2015

---

Sponsor:

IVI Valencia

[name]

[contact]

[[name] / [name]]

---

Principal Investigator:

[name]

Instituto Valenciano de Infertilidad

[contact]

[name]/[name]

---

Phase: Fase IV

---

Centros participantes:

IVI Valencia

---

Investigational Medicinal Product (IMP): Recombinant FSH, Highly Purified HMG, Ganirelix, Triptorelin

---

Primary Objective: To compare the serum concentrations of the different hormones involved in follicular steroidogenesis during an EOC cycle between FSHr and hpHMG.

---

Secundary Objectives:

- Define the area under the curve for each of the follicular steroids along the EOC in cycles stimulated with FSHr and hpHMG.
- Calculate the contribution to the circulation of each of the follicular steroids per unit of follicular volume.
- To identify the metabolic pathways of follicular steroidogenesis as a function of the type of gonadotrophin used for COC.
- To compare the concentration of steroids in follicular liquid in stimulated cycles with FSHr and hpHMG.
- Correlate the hormone levels observed in serum with the concentration in follicular fluid]

---

Methodology: 110 women will be included (55 in each study group, i) FSHr; ii) hpHMG) with normal ovarian function, who will follow ovarian stimulation in cycle with GnRH Antagonists. For greater uniformity in the study population, oocyte donors will be used.

Serum extractions and transvaginal ultrasound for folliculometry will be performed on the days of stimulation 1, 4, 6, 8 and the day of administration of the triptorelin. In the follicular puncture for the extraction of the oocytes, the first follicle will be individually aspirated to obtain the follicular fluid. The samples obtained will be frozen and stored at -80°C for later analysis.

In each serum sample they will be determined: Pregnenolone, Progesterone, 17-OH-Progesterone, Dehydroepiandrosterone, Androstenodione, Testosterone, Estrone and Estradiol.

Each day's hormone concentration will be compared between the two groups, so that the profile of each of the hormones can be defined for both stimulation protocols, and thus the follicular steroidogenesis profile. The area under the curve during ovarian stimulation will be calculated for each of the hormones included in the study, and both groups will be compared. The proportion of patients with elevated Progesterone on the last day of stimulation ( $>1.5$  ng/mL) will be compared between both groups.

Follicular fluid concentrations will be defined for each of the steroids analyzed, and the values between both groups will be compared, as well as their correlation with the levels observed in serum.

Clinical Trial Prospective randomized, open, parallel groups.

---

**Number of subjects: 110**

A previous study conducted by our group (Bosch et al, 2008) in which these two same protocols were compared in terms of clinical outcomes, showed that the serum P on the last day of stimulation was  $0.73 \pm 0.42$  in the HMG group vs  $0.99 \pm 0.48$  in the FSH group ( $p<0.001$ ). According to these data, to determine a difference of this magnitude with a 95% confidence level (5% alpha error) and 80% power (20% beta error), 48 patients per group are required. Assuming a loss rate of 15%, 55 patients should be randomly assigned to each group, i.e. 110 patients in total

---

**Inclusion criteria:**

- Women 18-35 years old
- Good state of psycho-physical health
- Normal menstrual cycle (25-35 days)
- Normal ovarian reserve, determined by an AMH=10-30 pMol/L
- BMI < 25.0
- Other criteria to be met by oocyte donors

---

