**Exclusion criteria:**

- Kidney failure
- Polycystic ovary
- BMI  $\geq 25.0$
- Any systemic or metabolic disorder that contraindicates the use of gonadotrophins.
- Any reason for exclusion from the oocyte donation program.

Test Product, Dose and Mode of Administration:

Arm 1:

*MEDICATION: Recombinant FSH*

*Therapeutic group: Gonadotrophins for ovarian stimulation*

*Route of administration: subcutaneous*

*Dose: 225 IU/day*

Arm 2:

*MEDICATION: Highly purified HMG*

*Therapeutic group: Gonadotrophins for ovarian stimulation*

*Route of administration: subcutaneous*

*Dose: 225 IU/day*

Reference Therapy, dose and Mode of administration:

---

Duration of study:

- Recruitment period: April 2016-July 2016
- Estimated end-of-treatment date of the last patient: October 2016
- End of study date: December 2016

---

Schedule of Assessments:

The patients will be recruited from the population of oocyte donors of the IVI Valencia programme. Patients will come to the clinic on their 2nd day of menstruation of the cycle in which ovarian stimulation is to be performed. At that time patients will be randomly assigned 1:1 to start COCs with 225 IU/day of FSHr (Gonal F) or hpHMG (Menopur). On the 6th day of stimulation, all patients will start a daily dose of 0.25 mg of the antagonist (Orgalutran), until the day of the final induction of oocyatic maturation. When at least 8 follicles reach a diameter of at least 17 mm, a bolus of 0.2 mg of triptorelin (Decapeptyl) should be administered. Follicular puncture will be performed 36 hours later, according to usual clinical practice.

Serum extractions and transvaginal ultrasound for folliculometry will be performed on the days of stimulation 1, 4, 6, 8 and the day of administration of the triptorelin, and the follicular liquid of the first aspirated follicle will be individually aspirated. The samples obtained will be frozen and stored at -80°C for later analysis.

Each serum sample shall be determined:

- Pregnenolone
- Progesterone
- 17-OH-Progesterone
- Dehydroepiandrostenodiona
- Androstenodione
- Testosterone
- Estrona
- Estradiol
- FSH
- LH

---

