### 2. Sample size

A previous study conducted by our group (Bosch et al, 2008) in which these two same protocols were compared in terms of clinical outcomes, showed that the serum P on the last day of stimulation was  $0.73 \pm 0.42$  in the HMG group vs  $0.99 \pm 0.48$  in the FSH group ( $p<0.001$ ). According to these data, to determine a difference of this magnitude with a 95% confidence level (5% alpha error) and 80% power (20% beta error), 48 patients per group are required. Assuming a loss rate of 15%, 55 patients should be randomly assigned to each group, i.e. 110 patients in total.

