### 3. Study Variables and Database

#### 3.1. Main variable:

Area under the serum progesterone curve during ovarian stimulation

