### 3.4. Descriptive variables:

- Age
- Body Mass Index
- Stimulation days
- Total dose of gonadotrophins
- Days with antagonist GnRH

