### 4.2. Intergroup homogeneity analysis:

Comparison of study groups from the point of view of basal and demographic characteristics using Student Test "t" after checking the assumption of normality using Levéne Variance Equality Test. In the case of non-parametric distribution, the Mann-Whitney test will be used.

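### AMH is needed from every woman for eligibility but is not named for reporting or adjustment, so a possible precision gain in the AUC comparisons is left unused

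*Combined protocol and SAP*

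**What the plan says.** The Synopsis, under Inclusion criteria, admits women with "Normal ovarian reserve, determined by an AMH=10-30 pMol/L". This is the only place where AMH appears.

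Allocation is described in the Synopsis under Schedule of Assessments: "patients will be randomly assigned 1:1 to start COCs with 225 IU/day of FSHr", or to hpHMG at the same dose. No stratification or minimisation factor is given, and AMH is not among the ten serum hormones listed there.

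The main variable in section 3.1 is "Area under the serum progesterone curve during ovarian stimulation". Sections 3.2 (secondary), 3.3 (control) and 3.4 (descriptive) do not list AMH. In 3.4 the only pre-treatment items are age and BMI. The others, such as "Total dose of gonadotrophins", accrue during stimulation.

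Section 4.2 plans a "Comparison of study groups from the point of view of basal and demographic characteristics" but does not name those characteristics. Section 4.3 compares hormone values and AUCs between arms by t-test or, if the values are not normal, by Mann-Whitney, and compares the proportion with elevated progesterone by chi-square. None of these analyses uses a covariate.

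**The concern.** The plan treats ovarian reserve as important enough to restrict entry by it, and the permitted range is still threefold (30/10). The plan also links follicles to circulating steroid: a secondary objective relates each steroid's contribution to follicular volume, and total follicular mass is a control variable. With the same stated dose in both arms and a trigger that depends on a follicle count, differences in ovarian response between women could plausibly add spread to the AUCs. A baseline marker of reserve is a natural candidate to explain part of that spread.

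Two things are at stake. If AMH does predict the AUC, leaving it out of the model keeps explainable variance in the error term and widens the confidence interval for the arm difference. And if AMH is not named for the baseline table, a reader may be unable to see how the arms compared on the plan's own marker of reserve.

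**Working it through.** **Inputs.** From section 2: last-day serum progesterone 0.73 (SD 0.42) with HMG and 0.99 (SD 0.48) with FSH, alpha 5%, power 80%, 48 per group. From the inclusion criteria: AMH 10-30 pmol/L. Assumed, because the documents give no value: the correlation r between AMH and the outcome within that range, taken as 0.1 to 0.5.

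**1. Reproduce the plan's figure.**
- Difference = 0.99 - 0.73 = 0.26.
- Pooled SD = sqrt((0.42² + 0.48²)/2) = 0.451.
- n per group = 2 × (0.451 × (1.960 + 0.842)/0.26)² = 47.2, so 48. This matches section 2 (two-sided test).
- Power at 48 per group = Φ(0.26/(0.451 × sqrt(2/48)) - 1.96) = Φ(2.824 - 1.96) = 80.6%.

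**2. Effect of adjusting for AMH.** The residual SD becomes 0.451 × sqrt(1 - r²), so n = 47.2 × (1 - r²) and power = Φ(2.824/sqrt(1 - r²) - 1.96).

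| Assumed r | n per group | Power at 48 per group |
|---|---|---|
| unadjusted | 48 | 80.6% |
| 0.1 | 47 | 81.0% |
| 0.2 | 46 | 82.2% |
| 0.3 | 43 | 84.2% |
| 0.4 | 40 | 86.9% |
| 0.5 | 36 | 90.3% |

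**3. Check by simulation** (20,000 trials, 48 per arm, AMH assumed uniform on 10-30). At r = 0.3, power was 79.5% unadjusted and 82.7% with ANCOVA. At r = 0.5 it was 80.5% and 89.9%. At r = 0 it was 79.6% and 79.1%, so an uninformative covariate costs about half a point.

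**4. Is the unadjusted test valid?** In the same simulation, the type I error of the unadjusted t-test was 5.3%, 4.9% and 4.9% for r = 0, 0.3 and 0.5. It stays at about 5% whether or not AMH predicts the outcome.

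**5. Size of a chance imbalance.** With AMH uniform on 10-30, SD = 20/sqrt(12) = 5.77. The 95% range for the difference in mean AMH is ±1.96 × 5.77 × sqrt(2/48) = ±2.3 pmol/L, or 0.40 SD. At the edge of that range, last-day progesterone would shift by r × 0.40 × 0.451: 0.02 ng/mL at r = 0.1, 0.05 at r = 0.3 and 0.09 at r = 0.5. The planned difference is 0.26.

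Steps 1, 2 and 5 concern last-day progesterone. They cannot be repeated for the main variable, because the documents give no SD for the progesterone AUC.

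**The case against.** The strongest reply is that nothing is broken. The trial is randomised, the unadjusted test holds its error rate, and the sample size was reached without AMH. The plan already limits heterogeneity by design: oocyte donors, age 18-35, BMI below 25, regular cycles, bounded AMH and no polycystic ovary. All of this stands. It makes covariate adjustment an improvement, not a repair.

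A reader might infer that a chance AMH imbalance would bias the result and pass for a gonadotrophin effect. The documents do not support that: the p-value and confidence interval already allow for chance imbalance (step 4). Nor do they say that reserve is the main determinant of follicle number, or that an imbalance would move all the steroid AUCs the same way.

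It would also be too strong to say that the AMH value is thrown away, or that 4.2 cannot show it. The wording of 4.2 is not confined to the list in 3.4 and may be meant to include AMH. The fair criticism is that AMH is unnamed, and a baseline table would not adjust the effect in any case.

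Other early measures exist. Follicular mass is defined at every ultrasound, including stimulation day 1, and the ten hormones are assayed that day. The documents do not say whether day-1 sampling precedes the first injection, so AMH is the more clearly pre-treatment choice, though not the only possible one.

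Finally, r could be small, and Mann-Whitney takes no covariate. Both are fair. The first is why the range starts at 0.1. The second means that the fix must state what replaces the fallback.

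**Conclusion.** The point holds as one of lost precision and incomplete specification, not of bias or invalidity. A baseline value that every participant must have is not specified for reporting or analysis. On last-day progesterone with 48 per group, using it would add between 0.4 power points (81.0 - 80.6, at r = 0.1) and 9.7 points (90.3 - 80.6, at r = 0.5). That is equivalent to 1 to 12 fewer patients per group. The low end is negligible and the high end substantial, and truncation of AMH to 10-30 pmol/L may lower r.

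The size rests on an assumed r, on a linear relation, and on an endpoint that is not the main variable. It should not be quoted as a gain for the progesterone AUC. What justifies the change is the very low cost, not a demonstrated large gain.

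**What to change.** - Section 3.4: add screening AMH as a baseline variable.
- Section 4.2: name AMH among the characteristics reported by arm.
- Section 4.3: for the progesterone AUC and the other AUCs, prespecify a linear model (ANCOVA) with arm and continuous AMH as terms, and report the adjusted difference with its 95% confidence interval. Where residuals are clearly non-normal, use log-transformed AUC or a rank-based ANCOVA, and state in advance which one applies. Keep the unadjusted test now planned as a sensitivity analysis.
- Stratifying the randomisation by AMH is optional. The point does not depend on it.

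The cost is SAP wording and one database field. Eligibility already requires the AMH result, so no extra samples or patients are needed.

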**Exclusion criteria:**

- Kidney failure
- Polycystic ovary
- BMI  $\geq 25.0$
- Any systemic or metabolic disorder that contraindicates the use of gonadotrophins.
- Any reason for exclusion from the oocyte donation program.

Test Product, Dose and Mode of Administration:

Arm 1:

*MEDICATION: Recombinant FSH*

*Therapeutic group: Gonadotrophins for ovarian stimulation*

*Route of administration: subcutaneous*

*Dose: 225 IU/day*

Arm 2:

*MEDICATION: Highly purified HMG*

*Therapeutic group: Gonadotrophins for ovarian stimulation*

*Route of administration: subcutaneous*

*Dose: 225 IU/day*

Reference Therapy, dose and Mode of administration:

---

Duration of study:

- Recruitment period: April 2016-July 2016
- Estimated end-of-treatment date of the last patient: October 2016
- End of study date: December 2016

---

Schedule of Assessments:

The patients will be recruited from the population of oocyte donors of the IVI Valencia programme. Patients will come to the clinic on their 2nd day of menstruation of the cycle in which ovarian stimulation is to be performed. At that time patients will be randomly assigned 1:1 to start COCs with 225 IU/day of FSHr (Gonal F) or hpHMG (Menopur). On the 6th day of stimulation, all patients will start a daily dose of 0.25 mg of the antagonist (Orgalutran), until the day of the final induction of oocyatic maturation. When at least 8 follicles reach a diameter of at least 17 mm, a bolus of 0.2 mg of triptorelin (Decapeptyl) should be administered. Follicular puncture will be performed 36 hours later, according to usual clinical practice.

Serum extractions and transvaginal ultrasound for folliculometry will be performed on the days of stimulation 1, 4, 6, 8 and the day of administration of the triptorelin, and the follicular liquid of the first aspirated follicle will be individually aspirated. The samples obtained will be frozen and stored at -80°C for later analysis.

Each serum sample shall be determined:

- Pregnenolone
- Progesterone
- 17-OH-Progesterone
- Dehydroepiandrostenodiona
- Androstenodione
- Testosterone
- Estrona
- Estradiol
- FSH
- LH

---

## Statistical Methods and Data Analysis

### 1. Population

It will include 110 women (55 in each study group) with normal ovarian function, aged between 18 and 35 years, who will follow ovarian stimulation in cycle with GnRH antagonists. For greater uniformity in the study population, oocyte donors will be used.

### 2. Sample size

A previous study conducted by our group (Bosch et al, 2008) in which these two same protocols were compared in terms of clinical outcomes, showed that the serum P on the last day of stimulation was  $0.73 \pm 0.42$  in the HMG group vs  $0.99 \pm 0.48$  in the FSH group ( $p<0.001$ ). According to these data, to determine a difference of this magnitude with a 95% confidence level (5% alpha error) and 80% power (20% beta error), 48 patients per group are required. Assuming a loss rate of 15%, 55 patients should be randomly assigned to each group, i.e. 110 patients in total.

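### At the stated 15% loss, 55 per group leaves about 47, one short of the 48 required; 55 keeps 48 only up to 7 losses (12.7%).

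*Combined protocol and SAP*

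**What the plan says.** The sample-size text in Section 2 is repeated in the synopsis under Number of subjects. It takes means and SDs of serum progesterone on the last day of stimulation from one of the sponsor group's previous studies: 0.73 (SD 0.42) with HMG and 0.99 (SD 0.48) with FSH. From these it concludes, "with a 95% confidence level (5% alpha error) and 80% power (20% beta error), 48 patients per group are required".

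The loss allowance follows directly: "Assuming a loss rate of 15%, 55 patients should be randomly assigned to each group, i.e. 110 patients in total".

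Section 1 (Population) and the Methodology entry of the synopsis repeat the resulting numbers without mentioning loss: "It will include 110 women (55 in each study group) with normal ovarian function" and "110 women will be included (55 in each study group". The documents do not say how the 15% was applied, do not define the loss rate in any other way, and contain no rule for replacing patients who are lost.

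**The concern.** A loss rate is ordinarily a share of the patients who enter. The number to randomise is then the evaluable number divided by the fraction retained. The step from 48 to 55 looks instead like an increase of 48 by 15%, which always gives too small a number.

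If so, the plan tells its reader that a 15% loss is covered when it is not, and the required number per group would be missed at the very loss rate the plan assumes. What is at stake is the accuracy of the justification and a small amount of power.

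**Working it through.** **Inputs, all from Section 2**
- Means 0.73 and 0.99, so the difference is 0.26.
- SDs 0.42 and 0.48.
- Alpha 5%. Sidedness is not stated; two-sided is assumed and checked in step 1.
- Power 80%.
- Required number 48 per group; loss rate 15%; 55 per group randomised, 110 in total.

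**Step 1: reproduce the 48**
- Common SD = √[(0.42² + 0.48²)/2] = √0.2034 = 0.451.
- Standardised difference = 0.26/0.451 = 0.5765.
- Normal approximation: n = 2 × SD² × (1.960 + 0.842)² / 0.26² = 47.23 per group, rounded up to 48.
- One-sided alpha would give 38, so the plan's figure is the two-sided one.

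The 48 reproduces, and the slip is confined to the loss step.

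**Step 2: the loss step**

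| Calculation | Result |
|---|---|
| Retained from 55 at 15% loss: 55 × 0.85 | 46.75 |
| Needed to keep 48 at 15% loss: 48/0.85 | 56.47, so 57 per group (114 in total) |
| Check: 57 × 0.85 | 48.45 |
| Adding 15% to 48: 48 × 1.15 | 55.2, rounded down to 55 |
| Largest loss that leaves 48 of 55 | 7/55 = 12.7% |
| One loss more | 8/55 = 14.5%, leaving 47 |

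The eighth loss in a group takes it below 48 while the loss rate is still under 15%. Even on the add-on reading, rounding 55.2 up would have given 56.

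**Step 3: effect on power**

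Difference 0.26, SD 0.451, two-sided 5%:

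| Evaluable per group | Normal approximation | t-test |
|---|---|---|
| 46.75 | 79.6% | 78.8% |
| 47 | 79.8% | 79.0% |
| 48 | 80.6% | 79.8% |

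By either method the shortfall costs about 1 percentage point (0.8 at 47, 1.0 at 46.75).

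**The case against.** The strongest case on the other side concedes the arithmetic and argues that it does not matter.

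- **The target was already rounded up.** The unrounded requirement is 47.23. Eight losses leave 47, a quarter of a patient short, with power of 79.8%, which rounds to the stated 80%. This is fair as a statement of size. But the plan commits to 48, and the expected 46.75 is below 47.23 as well.
- **48 is not a firm threshold.** Section 4.3 names the t-test, with Mann-Whitney as the fallback. By the t-test 48 gives 79.8%, and 49 is the first whole number to reach 80%. The inputs come from a single earlier study: if the SD were 10% lower or higher (an illustrative assumption), the requirement would be about 47.23 × 0.81 = 38 or 47.23 × 1.21 = 57. One patient is well inside that uncertainty. This stands, and it is why the point is minor.
- **The calculation is not for the main variable.** It uses last-day progesterone, while Section 3.1 names the area under the progesterone curve. So 47 against 48 says nothing direct about power for the main variable. This also stands, and the power figures here are limited to last-day progesterone for that reason.
- **Lowering the stated loss rate fits the assumption to the sample size.** The documents give no reason to expect less than 15% loss. This is a reasonable preference for keeping 15% and stating its consequence. Describing what 55 can absorb is still accurate, provided it is worded as a limit and not as a forecast.

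None of these makes the sentence correct as written.

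**Conclusion.** The concern holds. On the plan's own figures, 55 per group does not keep 48 evaluable at 15% loss: about 47 remain, and the loss that 55 can absorb is 7 patients per group, or 12.7%. The likely cause is multiplying by 1.15 instead of dividing by 0.85.

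The importance is low. Power for last-day serum progesterone falls by about 1 percentage point, to just under 80% by the normal approximation behind the 48. This is a correction to a stated figure, not evidence of an underpowered trial.

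The conclusion rests on two assumptions. The loss rate is read as a share of those randomised, falling equally on the two groups. Alpha is taken as two-sided, which is the only reading that reproduces 48.

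**What to change.** Keep 110 patients and correct the loss sentence in Section 2 and in the synopsis under Number of subjects. Either of these would do:

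- State that 55 per group tolerates up to 7 losses per group (12.7%) while leaving 48 evaluable.
- Keep the 15% assumption and state that about 47 per group would then remain, with power just under 80% by the normal approximation used for the 48.

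The second option leaves the sponsor's loss assumption untouched; the first makes the stated allowance slightly less favourable. Keeping both 48 and 15% would take 57 per group, four more patients in total (114 against 110), which is hard to justify for about 1 point of power.

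The cost is one sentence in two places. The figures of 110 and 55 in Section 1 and in the synopsis Methodology entry need no change.
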